2 BACKGROUND INFORMATION AND SCIENTIFIC RATIONALE

2.1 Background Information

The natural history of congenitally acquired CMV infection is well described.¹⁻⁷ In contrast, outcomes of perinatally and postnatally acquired CMV infections are less well characterized. It is generally agreed that postnatal acquisition of CMV in term infants does not lead to symptomatology or disease.⁸ In preterm infants, initial case reports suggested that peri- and postnatally acquired CMV infections could produce severe disease.⁹⁻¹⁴ Larger series and case-controlled trials more recently suggest that symptomatic disease in preterm babies is less common than asymptomatic infection, and long-term sequelae are rare.¹⁵⁻¹⁹ Nevertheless, severe disseminated CMV disease can occur in premature infants, including life-threatening pneumonitis, hepatitis, and thrombocytopenia.²⁰ Antiviral therapy in such patients is frequently used, albeit without either controlled data to demonstrate benefit or knowledge of proper dosing regimens.¹² In patients with symptomatic congenital CMV disease, six weeks of intravenous ganciclovir improves hearing outcomes in early childhood,²¹ and may benefit neurodevelopmental outcomes as well.²² In premature babies with visceral disease from postnatally acquired CMV, the goal of antiviral therapy is different; namely, it is to treat the end-organ disease, which is occurring at that time, rather than to prevent or improve long-term sequelae. Without efficacy data, the duration of treatment is variable, but anecdotal experience suggests that it generally is in the range of two to four weeks of total antiviral therapy. Approximately two-thirds of treated neonates receiving six weeks of intravenous ganciclovir develop Grade 3 or 4 neutropenia (utilizing the DAIDS Toxicity Tables) during therapy.²¹

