3.2.3 Exploratory Outcome Measures

Exploratory Endpoints:

- Correlation of ganciclovir plasma concentrations with neutropenia
- Detection of resistance to ganciclovir

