Both whole blood for CMV PCR and urine for CMV assessment will be obtained serially through Study Assessment Period 7 as long as the subject is receiving intravenous ganciclovir therapy (that is, until the ganciclovir is permanently discontinued). These specimens will be used to determine viral load and, as indicated, ganciclovir resistance. At each sample collection time, urine will be split into two aliquots. These aliquots will be available for CMV detection as appropriate, based upon whole blood viral loads. Specimens will then be available for subsequent testing for ganciclovir resistance in the UAB Virology Resistance Laboratory. Since ganciclovir is a renally excreted drug, serum creatinine will be drawn for the research protocol on the day that the ganciclovir pharmacokinetic specimens are obtained in order to calculate creatinine clearance using a method such as the modified Schwartz formula, and thus correlate ganciclovir clearance with renal function. Otherwise, data from hematology assessments (WBC count and differential, hemoglobin, platelet count) and from chemistry labs (serum creatinine, ALT, and AST) will be recorded on the study case report forms each study assessment period if they are being obtained for clinical reasons, but will not be drawn only for the purposes of the study. Ganciclovir dosing information (mg/dose, dosing interval, and subject weight) will be recorded on the day of the pharmacokinetic blood draws. Once a subject is successfully enrolled into the study the ganciclovir dosing information (mg/dose and dosing interval) will be recorded from the start of clinical treatment of ganciclovir until date of enrollment. After enrollment ganciclovir dosing information (mg/dose and dosing interval) will be captured from Study Assessment Period 1 through the Study Assessment Period 7; as long as the subject is receiving intravenous ganciclovir therapy.

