7.2 Enrollment/Baseline

7.2.1. Baseline Assessment (Period 1: Study Assessment Day 1 through Study Assessment Day 3, unless broader window specified)

- Confirm that informed consent has been obtained from parent or legally authorized representative
- Document baseline demographics (see Section 8.1.1; Window: Birth through Study Assessment Day 3)
 - Gestational age at delivery
 - Date of birth
 - Day of life at initiation of IV ganciclovir therapy
 - Gender
 - Race
 - Ethnicity
 - Birth weight
 - Weight at enrollment
 - Length in centimeters at enrollment
 - Reason ganciclovir being administered
 - Ganciclovir dose and dosing frequency
 - Manufacturer of the ganciclovir lot utilized at the treating facility
 - Date ganciclovir therapy was initiated
- Hematology labs (see Section 8.2; Window: Birth through Study Assessment Day 3)
 - WBC with differential, hemoglobin, and platelet count, if being drawn for clinical reasons; any laboratory value obtained during the window will suffice, with an effort being made to capture the most abnormal value
- Chemistry labs (see Section 8.2; Window: Birth through Study Assessment Day 3)
 - AST and ALT, if being drawn for clinical reasons; any laboratory value obtained during the window will suffice, with an effort being made to capture the most abnormal value

- Serum Creatinine (see Section 8.2.)
 - To be drawn on the calendar day that ganciclovir PKs are being drawn (Window: Study Assessment Day 1 through Study Assessment Day 5)
 - Required amount of whole blood for serum creatinine is 0.25 mL
- Ganciclovir pharmacokinetics (see Section 8.2.2.2.)
 - Ganciclovir concentrations will be obtained with one of the Study Assessment Dose 3, 4, 5, 6, 7, or 8 (Window: Study Assessment Day 1 through Study Assessment Day 5)
 - Timepoints for pharmacokinetic draws: 0h (immediately prior to IV ganciclovir dose; window: -15 min), 1h (immediately after the end of the IV ganciclovir dose; window: +15 min), 2-3h, 5-7h, and 10-12h
 - Required amount of whole blood for plasma ganciclovir determination at each timepoint is 200 μ L (0.2 mL)
- Virology specimens (see Sections 8.2.2.1.)
 - Blood for CMV quantitative PCR will be obtained (required amount of whole blood for CMV PCR is 0.5 mL)
 - If obtainable, urine for CMV detection will be collected non-invasively (e.g., bagged, from indwelling foley catheter, excess clinical specimen, etc.)
- Clinical treatment ganciclovir dosing information
 - mg/dose
 - Dosing interval
 - Patient weight

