A 95% confidence interval will be constructed to evaluate the mean changes in the log of the viral load between baseline (day 1) and weeks 1, 2, 3, 4, 5, and 6. Area under the curve will be calculated for each subject's CMV viral load measurement utilizing the trapezoidal rule. These AUCs will be calculated over the entire course of drug administration. Spearman's correlations will be given for each AUC estimation and also for the AUC after baseline viral load (VL) adjustment. Analysis of variance will be used to investigate whether grouping AUCs into groups (undetected, 100-1000, 1000-10000 and ≥ 10000) would indicate any PD relationships. In addition, changes in CMV viral load from baseline over time (weeks 1 through 6) will be correlated with PK parameters. These data will provide the framework for all PD analyses, where ganciclovir exposures variables will be correlated with the response variables using linear or maximum effect PD models.

Secondary analyses: To investigate the association of secondary outcomes namely, neutropenia, CMV in urine, viral load and resistance to ganciclovir, with plasma concentration, we will utilize inference methods based on Generalized Estimating Equations (GEE) which models repeated binary data. As in the primary analysis, GEE will enable us to compare groups, investigate changes of outcomes over time, and adjust for any covariates.

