A 95% confidence interval will be constructed to evaluate the mean changes in the log of the viral load between baseline (day 1) and weeks 1, 2, 3, 4, 5, and 6. Area under the curve will be calculated for each subject's CMV viral load measurement utilizing the trapezoidal rule. These AUCs will be calculated over the entire course of drug administration. Spearman's correlations will be given for each AUC estimation and also for the AUC after baseline viral load (VL) adjustment. Analysis of variance will be used to investigate whether grouping AUCs into groups (undetected, 100-1000, 1000-10000 and ≥ 10000) would indicate any PD relationships. In addition, changes in CMV viral load from baseline over time (weeks 1 through 6) will be correlated with PK parameters. These data will provide the framework for all PD analyses, where ganciclovir exposures variables will be correlated with the response variables using linear or maximum effect PD models.

Secondary analyses: To investigate the association of secondary outcomes namely, neutropenia, CMV in urine, viral load and resistance to ganciclovir, with plasma concentration, we will utilize inference methods based on Generalized Estimating Equations (GEE) which models repeated binary data. As in the primary analysis, GEE will enable us to compare groups, investigate changes of outcomes over time, and adjust for any covariates.

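### Exposure–neutropenia: the only named analysis is a repeated yes/no GEE; adding a neutrophil-count model would recover information at little cost

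*Protocol*

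**What the plan says.** Protocol 11.4, under secondary analyses, gives the aim as "To investigate the association of secondary outcomes namely, neutropenia, CMV in urine, viral load and resistance to ganciclovir, with plasma concentration" and continues: "we will utilize inference methods based on Generalized Estimating Equations (GEE) which models repeated binary data". SAP Appendix B uses the same text. Neither document names an analysis of the neutrophil count itself.

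Viral load stands in the same sentence but is treated more fully. The paragraph before it plans confidence intervals for log change, a trapezoidal area under the curve and Spearman correlations. That paragraph ends with a general statement on pharmacodynamic (PD) analyses, "where ganciclovir exposures variables will be correlated with the response variables using linear or maximum effect PD models", which follows the viral-load text and does not mention neutrophils.

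The count can be derived from data already on the case report form. Protocol 7.2.1 records "WBC with differential, hemoglobin, and platelet count, if being drawn for clinical reasons", and the later periods do the same. Any value in the window is accepted, with a preference for the most abnormal. Protocol 4 limits availability: these tests are recorded if obtained clinically "but will not be drawn only for the purposes of the study".

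On status, Protocol 3.2.3 lists "Correlation of ganciclovir plasma concentrations with neutropenia" as an exploratory endpoint, while 11.4 and SAP Appendix B call neutropenia a secondary outcome. The analysis plan sets no neutropenia cut. The DAIDS grades appear in Protocol 2.1, as background, and the DAIDS table appears in SAP section 10, as a guide to event names.

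**The concern.** A yes/no analysis treats a count just under the cut the same as a near-absent count, and treats any fall that stays above the cut as no response. In a study of about 32 infants, that discards information the study already holds.

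The relation matters because Protocol 2.2 expects the data to help limit toxicity in later infants, and neutropenia is the only drug toxicity among the objectives in Protocol 3.1. A non-significant binary result in so few infants could be read as showing no link between exposure and neutrophils when the analysis had little chance of finding one.

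**Working it through.** **The plan's only power figure.** Protocol 11.2 gives 83% for the AUC12 comparison (means 20, 20, 30, 35; SD 10; four groups of 8; 5% level). The SD of the means is √(168.75/4) = 6.50, so f = 0.65 and λ = 32 × 0.65² = 13.5. With 3 and 28 degrees of freedom the power is 83.1%, so the figure reproduces. It says nothing about neutropenia, for which no effect size or power is stated.

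**Inputs for neutropenia.**
- n = 32 (Protocol 11.2).
- Rate p = 2/3: the background figure in Protocol 2.1 for infants who "develop Grade 3 or 4 neutropenia (utilizing the DAIDS Toxicity Tables) during therapy". It is cumulative over six weeks in other neonates, so it is only a working value here.
- Assumptions: log(ANC) roughly normal; correlation r with log exposure 0.2 to 0.7; one value per infant; two-sided 5% test.

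**Information kept by a cut.** The relative efficiency is ARE = φ(z)²/[p(1−p)], where z is the normal quantile at p. At p = 2/3, z = 0.431 and φ(z) = 0.364, so ARE = 0.132/0.222 = 0.595.

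| Rate p | ARE | Information lost |
|---|---|---|
| 0.5 (best case) | 0.637 | 36% |
| 2/3 | 0.595 | 40.5% |
| 0.3 | 0.576 | 42% |
| 0.2 | 0.490 | 51% |
| 0.1 | 0.342 | 66% |

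At p = 2/3, 32 infants carry the information of 32 × 0.595 ≈ 19.

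**Power.** By the Fisher-z test, power ≈ Φ(atanh(r)·√(n−3) − 1.96). For the cut outcome, either replace r by r·√0.595 = 0.771r, or replace n by 19. Example at r = 0.5: full scale 0.549 × √29 − 1.96 = 1.00, power 84%; cut 0.407 × √29 − 1.96 = 0.23, power 59%.

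| r | Count | Yes/no | Loss by formula (points) | Loss by simulation (points) |
|---|---|---|---|---|
| 0.2 | 19% | 13% | 6–7 | 6 |
| 0.3 | 38% | 24% | 14–15 | 15 |
| 0.4 | 63% | 40% | 22–23 | 23 |
| 0.5 | 84% | 59% | 25 | 24 |
| 0.6 | 96% | 77–79% | 17–19 | 17 |
| 0.7 | >99% | 90–93% | 6–10 | 6–7 |

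The simulation compares correlation t tests on the full and the cut scale, with one value per infant.

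**Sensitivity.**
- A logistic likelihood-ratio test for the cut outcome gave 44%, 64% and 83% at r = 0.4, 0.5 and 0.6, slightly more than the t test, but with 6% type I error.
- Four-period GEE, Gaussian against binomial (intraclass correlation 0.5, p = 0.3 and 2/3, r = 0.3 to 0.5, 250 runs per setting): loss 8 to 21 points. With 250 runs, one power estimate near 50% has a standard error of √(0.25/250) ≈ 3 points.
- If only 24 infants had counts (assumed), at a rate of about two-thirds: 51% vs 32%, 73% vs 48% and 90% vs 66% at r = 0.4, 0.5 and 0.6.
- At a 20% rate with n = 32 and r = 0.5: 86% vs 51%, a loss of 35 points.

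**The case against.** **The power loss is not fixed by the documents.** A reader might take the correlations of 0.4 to 0.7 tabulated in Protocol 11.2 and infer one definite power penalty. That table serves the gestational-age fallback for AUC12, not exposure and ANC, and the two-thirds rate comes from another study. This objection stands: the loss can only be given as a range under stated assumptions.

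**A continuous route is not excluded.** A reader might infer that the plan bars any count-based analysis. The general PD sentence in 11.4 leaves room for one, so the binary GEE is the only *named* analysis, not the only possible one. Since that sentence never mentions neutrophils, the gap in specification remains.

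**The question asked is about developing neutropenia.** Protocol 3.1 words the objective that way, and a slope on log(ANC) answers a different question from the risk of a clinical grade. This stands as a reason to keep the binary analysis. It is no reason to omit the other.

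**The counts are imperfect.** They come from clinically triggered draws and mix arbitrary values with worst values, and log(ANC) is undefined at zero. The first limit affects the yes/no analysis as well, since it uses the same values. The second needs a stated rule.

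**One value per infant is not the planned model.** That is true, and the repeated-measures simulation gave a somewhat smaller loss. However, exposure is profiled once per infant, with an optional second profile in Period 4, so the contrast is largely between infants.

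**Conclusion.** This is a cheap improvement to an exploratory analysis. The plan names only a repeated yes/no model for exposure and neutropenia, although counts will be available wherever they are drawn clinically. Under normality on the log scale, any cut loses at least 36% of the information, and about 40% at a two-thirds rate. With 32 infants, one value each, that rate and assumed correlations of 0.2 to 0.7, the cost is roughly 6 to 25 points of power. The four-period GEE simulation gave about 8 to 21 at correlations 0.3 to 0.5. Lower rates cost more, and fewer than 32 infants may contribute counts.

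A reader might infer that the trial forfeits a powered safety test. The documents do not support that: the endpoint is exploratory in Protocol 3.1 and 3.2.3, and no power was claimed for it.

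**What to change.** In Protocol 11.4 and SAP Appendix B:

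1. Add a linear mixed model of log(ANC) by period on log exposure, with infant as random effect and baseline ANC as covariate.
2. State a rule for zero counts, for example a floor at the lowest reportable value.
3. State that the recorded count is the most abnormal in the period where available, and that counts come from clinical draws.
4. Keep the binary GEE and the proportion with graded neutropenia alongside the new model, because the objective concerns development of neutropenia.

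The cost is one extra model and a few lines of text, with no new blood or data. The drawback is that the added result is on the ANC scale and gives no risk of a clinical grade, which is why the binary results stay. Clinically triggered sampling remains a limit of both analyses.

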The appropriate dose of intravenous ganciclovir for premature babies has not been studied. Previous studies of ganciclovir have indicated that the area-under-the-concentration curve (AUC) of ganciclovir is most closely related to virologic treatment success.²³ Data from an National Institute of Allergy and Infectious Diseases (NIAID) CASG Phase II study of intravenous ganciclovir (6 mg/kg/dose q 12 hrs) in term neonates with symptomatic congenital CMV disease revealed a median AUC₁₂ of 27 μ gxh/mL (mean AUC₁₂=32.3+13.7 μ gxh/mL, range 17.2 to 55.9 μ gxh/mL, n=13).²⁴ A more recent CASG investigation of oral valganciclovir included comparative pharmacokinetic data following 6 mg/kg/dose every 12 hrs of intravenous ganciclovir. The mean AUC₁₂ in young neonates (median age: 16.5 days) on the second day following study enrollment was 38.2 μ gxh/mL (median: 25.5 μ gxh/mL), but the coefficient of variation was large (112).²⁵ In five neonates in whom pharmacokinetic sampling was performed on day 4 and day 34 of intravenous ganciclovir therapy, ganciclovir clearance nearly doubled and AUC₁₂ reduced by almost half over the 30 day interval,²⁵ suggesting that maturational changes may be occurring rapidly in early life which may affect ganciclovir dosing. No data exist on ganciclovir dosing in very premature babies, who are at greatest risk for CMV disease.

due to the absence of transplacental antibodies. Notably, acyclovir must be dose-adjusted based upon renal function such as that which can occur with prematurity.²⁶

The CASG and the UAB Central Unit have had significant success in performing multi-center pharmacokinetic and pharmacodynamic studies with both ganciclovir and valganciclovir in infants during the first month of life.^{21,22,25,27-30} In this study, this experience will be utilized to further define the utility of this drug in very premature children.

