3 OBJECTIVES

3.1 Study Objectives

Primary:

- To define the pharmacokinetics of ganciclovir in premature (< 32 weeks gestational age at birth) infants

Secondary:

- To assess changes in quantitative viral DNA in whole blood as a function of ganciclovir pharmacokinetics
- To assess clearance of CMV in urine as a function of ganciclovir pharmacokinetics

Exploratory:

- To assess development of neutropenia as a function of ganciclovir pharmacokinetics
- To determine the potential for the development of resistance to ganciclovir as a function of pharmacokinetics, dose, age, and duration of therapy

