The amplification efficiency is calculated to be 1.95 with the theoretical maximum of 2.0, which would indicate a doubling with each PCR cycle. Each assay contains a No Target Control and inhibition is monitored using a house-keeping gene, human albumin. This 2 primer set assay has been used for several previous studies and has been utilized in the Children's Diagnostic Virology Laboratory for 2 years, primarily to monitor transplant patients. The Diagnostic Laboratory participates in the College of American Pathologists, CAP, quantitative unknowns for CMV, EBV and BK viruses. Over the last 3 cycles, the CMV assay has been within 4 fold of the mean for these unknowns and has improved with each group.

Antiviral resistance will be performed in the UAB Viral Resistance Laboratory. Lab testing of viral isolates for ganciclovir resistance will be conducted by a standing SOP with a fully characterized assay.

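### Resistance goes into a repeated-binary GEE with no rule for visits without virus, so the exposure odds ratio rests on an unstated coding choice and its test is unreliable with few events in 32 infants

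*Protocol*

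**What the plan says.** - **Objective and endpoint.** Protocol 3.1 lists among the exploratory objectives: "To determine the potential for the development of resistance to ganciclovir as a function of pharmacokinetics, dose, age, and duration of therapy". The endpoint in 3.2.3 is "Detection of resistance to ganciclovir". Neither says what value an infant or visit without virus receives.
- **Assay.** Protocol 8.2.1.1: "Lab testing of viral isolates for ganciclovir resistance will be conducted by a standing SOP with a fully characterized assay".
- **When it is run.** Protocol Section 4: "These specimens will be used to determine viral load and, as indicated, ganciclovir resistance". No criterion for the indication is given. The Protocol Summary (Description of Study Design) states the same use of the specimens without that condition.
- **Urine.** Section 4 says of the stored aliquots: "These aliquots will be available for CMV detection as appropriate, based upon whole blood viral loads". The second specimen source may therefore also depend on viral response.
- **Analysis.** Protocol 11.4 covers resistance together with three other outcomes: "neutropenia, CMV in urine, viral load and resistance to ganciclovir, with plasma concentration, we will utilize inference methods based on Generalized Estimating Equations (GEE". It describes the method as a model for binary outcomes measured repeatedly. SAP Appendix B has the same text. Both call these outcomes secondary, although Section 3 classes neutropenia and resistance as exploratory.
- **Follow-up.** Under Appendix A, Periods 2 to 7 are sampled only while ganciclovir continues.

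**The concern.** Neutropenia can be read from any available blood count. Resistance cannot: without virus there is nothing to test. Whether a visit has a result depends on whether virus persisted, and the plan itself expects exposure to influence that. Section 2.1 reports that "the area-under-the-concentration curve (AUC) of ganciclovir is most closely related to virologic treatment success". If resistant virus also persists longer than sensitive virus, the scored visits are selected on a consequence of both the exposure and the outcome.

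The second difficulty is sparseness. The test relies on a robust variance from 32 infants, of whom only a few are likely to show resistance. That is a poor setting for GEE standard errors, however visits without virus are handled.

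At stake is the reading of one exploratory result. The study could report an association between exposure and resistance, in either direction, that comes from the coding or from the variance estimate.

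**Working it through.** **Inputs.** The documents give no figure for the resistance analysis, so there is none to reproduce, and they give no rates for resistance or clearance; all such rates below are assumed. From Protocol 11.2 come n = 32 and the AUC12 planning values (means 20, 20, 30, 35; SD 10), which supply the exposure distribution for the first simulation. As a check on those inputs, a noncentral F calculation gives power of 96.2%, 90.6%, 83.1% and 74.7% for SD 8, 9, 10 and 11, matching the stated 96%, 91%, 83% and 75%.

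**Step 1. Scored visits only, closed form.** Let resistance have the same rate *r* at high and low exposure, so the true odds ratio is 1. Let R and S be the probabilities of recovering virus when it is resistant or sensitive. Then:

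- resistance among scored visits = rR / [rR + (1 − r)S]
- odds ratio, high versus low = (R_high / S_high) / (R_low / S_low), which does not depend on *r*.

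| S, low → high exposure | R, low → high exposure | Odds ratio |
|---|---|---|
| 60% → 30% | 90% → 90% | (0.90/0.30)/(0.90/0.60) = 2.00 |
| 60% → 30% | 80% → 70% | (0.70/0.30)/(0.80/0.60) = 1.75 |
| 70% → 50% | 90% → 85% | (0.85/0.50)/(0.90/0.70) = 1.32 |
| 50% → 20% | 90% → 90% | (0.90/0.20)/(0.90/0.50) = 2.50 |
| 60% → 30% | 60% → 30% | 1.00 |

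In the first row with r = 10%, scored resistance is 0.09/0.63 = 14.3% at low exposure and 0.09/0.36 = 25.0% at high exposure.

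**Step 2. Visits without virus coded as not detected.** The detected proportion is now rR. With r = 10%:

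- R 90% at both exposures: 9% versus 9%, odds ratio 1.00.
- R 80% → 70%: 8% versus 7%, odds ratio (0.07/0.93)/(0.08/0.92) = 0.87.
- R 60% → 30%: 6% versus 3%, odds ratio (0.03/0.97)/(0.06/0.94) = 0.48.

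The same data can therefore give an odds ratio above or below 1, depending on a rule that the plan does not state.

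**Step 3. Large-sample GEE.** Logistic GEE, independence working correlation, robust standard errors, seven periods, 20,000 infants. Assumed: 5% resistant at baseline and 1.5% new per period, unrelated to exposure. Odds ratios are per 10 AUC units; with status known at every visit they were 1.01 to 1.03.

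| Behaviour of resistant virus | Scored visits only | Coded not detected |
|---|---|---|
| Persists whatever the exposure | 1.53 | 1.02 |
| Half as sensitive to exposure | 1.41 | 0.95 |
| Clears like sensitive virus | 1.00 | 0.71 |

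If clearance does not depend on exposure at all, the scored-only value is 1.01.

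**Step 4. Behaviour at n = 32.** In 400 simulated trials per scenario, with about four resistant infants each, the scored-only GEE rejected at nominal 5% in 31% (first row of Step 3) and 26% (second row). With full status known, rejection was still 15% and 17%. That part is small-sample error and owes nothing to selection.

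A second simulation had about two to three infants with resistance detected and underlying resistance again unrelated to exposure. The GEE rejected in 27–33% of trials whether visits without virus were omitted or coded negative. Once-per-infant Firth logistic regression rejected in 3–5%.

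**The case against.** **The endpoint wording may already settle the coding.** Detection of resistance can be read as detected or not detected, so a visit without virus would count as not detected and nobody is lost. That reading is fair. A reader might infer that infants who clear virus leave the resistance analysis, but the documents do not say so; it follows only if the GEE is fitted to available results. Neither reading is written down, and the sparse-event problem remains under both.

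**The upward bias is conditional.** It needs exposure-driven clearance and lesser clearance of resistant virus together. Without either, the scored-only odds ratio stays at about 1. A claim that the plan will produce a false link between exposure and resistance is therefore too strong.

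**The number of infants affected is easily overstated.** With 10% resistance, resistant virus always persisting, and clearance of sensitive virus of 70% and 30% in two halves of 16 infants, a reader might compute 16 × 0.9 × (0.7 + 0.3) = 14.4 of 32 unscored. That describes one week. An infant who clears virus later still contributes earlier visits to a seven-period GEE, so the figure should not be used. Nor does the undetected category in 11.4 show that the plan expects unscored infants: it groups viral-load AUCs, and urine may yield virus when blood does not.

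**Missing outcomes need not bias a GEE.** True where missingness depends only on modelled covariates. Here it would also depend on whether the virus is resistant, which covariate adjustment does not remove.

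**Other test routes may exist.** The closure checklist in SAP Appendix G mentions culture and sequencing, and a laboratory SOP outside these documents may define testing triggers. Sequencing still needs viral DNA, and an SOP would not settle the statistical denominator.

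**Conclusion.** The concern holds in a limited form. The plan names a model for resistance without defining who is evaluable or how a visit without virus is coded, and that choice can move the odds ratio in either direction from a true value of 1. In the cases worked, scored-only odds ratios run from 1.00 to 2.50 for high versus low exposure; coding visits without virus as not detected gives 0.48 to 1.00. These ranges illustrate assumed rates and do not predict this trial's result.

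The firmer part is the type I error. With 32 infants and a handful of resistant ones, the planned GEE rejects several times too often under either coding, and by a factor of about three even when status is fully known (15–17% against 5%). The exact level depends on the assumed rates and number of events.

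The endpoint is exploratory and primary AUC12 is untouched. A reader might go further and see a threat to the study's dosing conclusions, but Protocol 2.2 ties those to pharmacokinetics and toxicity. This is a low-cost improvement and does not invalidate the plan.

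**What to change.** In Protocol 11.4 and SAP Appendix B:

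1. Take resistance out of the GEE and label it exploratory, as in Section 3.
2. Score it once per infant: detected if any tested on-study specimen is resistant, otherwise not detected. The denominator is all infants with PK data and at least one virus-positive on-study or entry specimen. Counting the entry specimen keeps early clearers in, since treatment may start before enrollment.
3. Relate the outcome to AUC12 by exact or Firth logistic regression.
4. Reconcile the Protocol Summary with Section 4, so that at least the last stored virus-positive specimen of every infant is tested whatever the response.
5. Report by exposure the number of infants with no testable virus and the time on drug at the tested specimen, because fast clearers are tested earlier. Add a sensitivity analysis restricted to infants with a resistance result.
6. State that the outcome is resistance *detected*, so a lower rate at higher exposure may reflect clearance, and that timing and duration of therapy are described and not modelled.

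**Cost.** Wording changes, plus at most about 32 runs of an assay already planned, on stored specimens with no new sampling. What is lost is a model for duration of therapy, which the objective names; with so few events the GEE could not estimate it reliably.
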